DISSEMINATION: Share AYA educational material via implementation toolkits (R01 CA218389-01) & Post material on www.cancersurvivorlink.org educational platform & share with registrants via email

For Aim 3, eligible stakeholders will be recruited (N=20 AYA survivors) via phone or in clinic by a member of the Aflac Cancer Survivor Research team, and survivors interested in participating will be verbally consented via WebEx. Example questions are outlined in Table 3. These stakeholder reviews will be used to inform revisions to the infographics and videos, which will be made prior to engaging in Aim 4.

For Aim 3 and 4, all interviews will be recorded for transcription/qualitative data analysis.

The consent and interview processes in Aim 3 will be completed sequentially during the subject's webex interview; therefore, this consent discussion will be recorded. All Aim 3 subjects must verbally consent to this recording prior to the recorded consent process. Once the subject has consented to recording, the recording will begin. The study staff will follow Aim 3 telephone scripts for the entire consenting process. Telephone scripts for Aim 3 are included in this protocol.

Once the interview recording begins, study staff will ask if the subject has provided recording consent (for documentation purposes). Next, all subjects will have to confirm their identity (for security and data validity purposes) by providing their name and date of birth. The information provided by the subject must match the information gathered in Epic for the main study consenting to begin. Subjects will then go over the main study and verbally consent for their participation in it.

For Aim 4, we will recruit a total of N=58 AYA survivors to evaluate our revised electronic educational materials (eligibility requirements described above). Recruitment procedures will be the same as in Aim 3 except that in Aim 4, subjects will review and complete consent online as in Aims 1 & 2. The initial page of the REDCap survey will contain a brief online consent outlining the purpose of the study, its voluntary nature, time commitment,

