No biological specimens will be collected as part of this research. Participants' electronic medical records will be reviewed to abstract treatment data. Confidentiality within this study will be rigidly maintained. Computer files will use study identification numbers only and are password protected. Only necessary personnel will have access to any of these files. Based on existing best practices for security and privacy in health information technology, we will identify the technologies and features to be employed to ensure privacy and security of personal information. This will address identity and access management, secure storage, secure messaging, encryption, and other security technologies and approaches.

VI. Statistical Analysis Plan

Aims 1 & 2: In 2015, the Aflac Cancer Survivor Program (Aflac CSP) saw over 200 AYA survivors aged 18-22 years (Aim 1). Additionally, the Aflac CSP has transitioned approximately N=165 survivor patients since 2013 (Aim 2). Based on our previous research with survivor patients > 18 years of age, we estimate that less than 2% of AYAs will be non-English speakers. During the year-long study period, we anticipate that there will be at least N=200 AYA patients who are eligible for participation in Aim 1 and at least N=160 AYA patients who are eligible for participation in Aim 2. Previous studies with our AYA population have yielded initial recruitment rates and retention rates above 80%. Of the eligible AYA patients, we estimate that 75% [Aim 1: N=220 patient-parent dyads (440 participants), Aim 2: N=120 patient-parent dyads (240 participants), Aim 3: N= 20 patients, Aim 4: N=58] will participate in each aim of the study. In our univariate analysis, these sample sizes provide us with at least 80% or greater power to detect correlations of magnitude ≥ 0.25 and odds ratios of at least 2.5, depending on the prevalence of the risk factor, assuming that approximately 20-30% of patients meet our definition of successful transition. Power analyses were conducted using PASS v. 11 (Kaysville, UT) using a two-sided test for a single correlation and a two sample Z-test for proportions. Given these anticipated numbers, we can assess at most 15 possible predictors for aim 1 and 12 predictors for aim 2 to ensure that we have at least 10 observations per predictor in our principal component analysis.

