Aims 3 & 4: Qualitative data analysis should be conducted until data “saturation”, or the point at which no new information is likely to be garnered from additional interviews/focus groups. Given that previous research has indicated that over 85% of analytic themes are identified within the first 12 interviews, we are confident that we will reach saturation of new information with N=20 stakeholder interviews with AYA survivors in Aim 3, as well as N=25 AYA post-test interviews in Aim 4. In order to analyze our qualitative data, separate codebooks for analyzing data will be developed at each stage of the formative evaluation using thematic analyses based on guide questions and evaluation attributes. Following development of the codebooks, each response will be coded by two independent raters. Open coding methods will be used to analytically evaluate the data and comparisons will be made for data similarities and differences. A qualitative analysis software package, NVivo, will be used to assist in the identification of patterns and relationships between concepts (i.e., acceptability, appropriateness). Frequencies of all codes will be tabulated and used to inform the revision of the electronic educational materials by types. Differences in the frequency of codes will be examined among subgroups of AYA small group participants (i.e., age, years post diagnosis, gender) using Chi-square and ANOVA analyses. Our team and the Winship Cancer Institute’s Intervention Development, Dissemination and Implementation (IDDI) core has vast experience with qualitative and mixed methods analyses.

In Aim 4, paired t-tests or Wilcoxon signed-rank tests will be used to compare AYA HBM constructs and knowledge about survivor care and late-effects before and after reviewing the electronic educational material. Given 58 AYA survivors, we will have greater than 80% power to detect an average of a 1.5 point increase (or an effect size of 0.40) in AYA average knowledge score after reviewing the electronic educational materials.

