After data are exported from REDCap, we will perform data cleaning and run descriptives on all variables. We will analyze pre and posttest differences on knowledge, HBM constructs, self-efficacy and intentions using paired t-tests. Reliability analyses will be run for scales. Differences in HBM constructs, knowledge, PAM activation, and self-efficacy to manage cancer care and demographic or cancer history will be assessed by ANOVAs or independent t-tests to test moderator effects. Power was calculated using a paired t-test with an assumed standard deviation of paired difference of 4.0 points using a 0.05 level of significance and a medium correlation between pre- and post-test.

VII. References

DeSantis, C.E., et al., *Cancer treatment and survivorship statistics, 2014*. CA Cancer J Clin, 2014. **64**(4): p. 252-71.

Mertens, A.C., et al., *Cause-specific late mortality among 5-year survivors of childhood cancer: the Childhood Cancer Survivor Study*. J Natl Cancer Inst, 2008. **100**(19): p. 1368-79.

Group, C.s.O., *Long-term follow-up guidelines for survivors of childhood, adolescent and young adult cancers*, 2008, Children's Oncology Group: Arcadia, CA.

Klosky, J.L., et al., *Factors influencing long-term follow-up clinic attendance among survivors of childhood cancer*. Journal of Cancer Survivorship, 2008. **2**(4): p. 225-32.

Barakat, L.P., et al., *Factors that contribute to post-treatment follow-up care for survivors of childhood cancer*. Journal of Cancer Survivorship, 2012. **6**(2): p. 155-162.

Oeffinger, K.C., *Longitudinal risk-based health care for adult survivors of childhood cancer*. Current Problems in Cancer, 2003. **27**(3): p. 143-167.

Eshelman-Kent, D., et al., *Cancer survivorship practices, services, and delivery: a report from the Children's Oncology Group (COG) nursing discipline, adolescent/young adult, and late effects committees*. Journal of Cancer Survivorship, 2011. **5**(4): p. 345-357.

Oeffinger, K.C. and W.H. Wallace, *Barriers to follow-up care of survivors in the United States and the United Kingdom*. Pediatr Blood Cancer, 2006. **46**(2): p. 135-42.

Patenaude, A.F. and M.J. Kupst, *Psychosocial functioning in pediatric cancer*. Journal of Pediatric Psychology, 2005. **30**(1): p. 9-27.

Heirs, M., et al., *A systematic review of models of care for the follow-up of childhood cancer survivors*. Pediatric Blood & Cancer, 2013. **60**(3): p. 351-356.

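### The Aim 4 power statement counts all 58 survivors to be recruited as complete pre/post pairs and leaves no allowance for loss before the post-test

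*Combined protocol and SAP*

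**What the plan says.** Section III.C (Procedures & Recruitment) sets the Aim 4 target: "For Aim 4, we will recruit a total of N=58 AYA survivors". These survivors consent online, take the pre-test and review the materials. They are then scheduled for a post-test two weeks after the review, with up to five reminders. Table 1 also puts N=58 beside the pre-test and post-test step, and Section VI (Aims 1 & 2) lists 58 among those expected to participate.

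Section VI (Aims 3 & 4) uses the same number for power: "Given 58 AYA survivors, we will have greater than 80% power to detect an average of a 1.5 point increase". It describes the target as "an average of a 1.5 point increase (or an effect size of 0.40"). The basis follows: "Power was calculated using a paired t-test with an assumed standard deviation of paired difference of 4.0 points". Alpha is set at 0.05, and the pre/post correlation is called medium without a value.

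The only retention figure in the document is in the Aims 1 & 2 text: "Previous studies with our AYA population have yielded initial recruitment rates and retention rates above 80" per cent. For Aim 4 there is no dropout allowance, no target number of completed pairs, no replacement rule and no rule for a missing post-test.

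**The concern.** The unit of analysis in a paired t-test is the complete pair. A survivor who consents but does not finish the initial queue, or does not return for the post-test, contributes nothing to it. The plan foresees such losses, since it provides for reminders and for staff contact when the queue is left unfinished. Yet the power statement carries the recruitment number over unchanged.

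Knowledge gain is A4 Hypothesis 1 and the only Aim 4 outcome with a stated power. If pairs are lost, a non-significant result would be read against a power that the analysed sample did not have.

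**Working it through.** **Inputs from the plan.** Mean gain 1.5 points; effect size also given as 0.40; SD of paired difference 4.0; alpha 0.05; paired t-test; n = 58 (all Section VI, Aims 3 & 4); 58 recruited (Section III.C). The unspecified medium correlation is not needed once the SD of the difference is fixed.

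**Assumptions.** (a) The test is two-sided. Sidedness is not stated for Aim 4; the Aims 1 & 2 calculation uses a two-sided test for the correlation. (b) The loss rates are illustrative, because the documents give no completion rate for Aim 4.

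**Formula.** With d = gain / SD of difference, the test statistic follows a noncentral t distribution with n − 1 degrees of freedom and noncentrality d × √n. Power is the probability that it falls beyond the two-sided 5% critical value.

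**Step 1: reproduce the plan's figure.** d = 1.5 / 4.0 = 0.375. At n = 58 the noncentrality is 0.375 × √58 = 2.856, the critical value is 2.002 and power is 0.802. The claim of more than 80% is reproduced for 58 complete pairs.

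**Step 2: look for slack.** At n = 57, noncentrality is 2.831 and power is 0.795. So 58 is the minimum number of pairs for 80%.

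**Step 3: power with fewer pairs, two-sided 0.05.**

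| Complete pairs of 58 | Approximate loss | Power, d = 0.375 | Power, d = 0.40 | Gain detectable with 80% power (SD 4.0) |
|---|---|---|---|---|
| 58 | none | 0.802 | 0.850 | 1.50 |
| 57 | 2% | 0.795 | 0.843 | 1.51 |
| 55 | 5% | 0.780 | 0.830 | 1.54 |
| 52 | 10% | 0.756 | 0.808 | 1.58 |
| 49 | 15% | 0.730 | 0.783 | 1.63 |
| 46 | 20% | 0.702 | 0.756 | 1.69 |

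Pairs are rounded down: 80% of 58 is 46.4. With 47 pairs the powers are 0.711 and 0.766.

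**Step 4: other readings of the plan.** The two stated targets are not the same: 1.5 / 4.0 is 0.375, while 0.40 implies a gain of 0.40 × 4.0 = 1.6 points or an SD of 1.5 / 0.40 = 3.75. Under 0.40 the minimum is 52 pairs (0.808; 51 pairs give 0.7999), so six losses are tolerable (6/58 = 10%). With a one-sided test at d = 0.375, 46 pairs would suffice (0.805).

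**The case against.** The strongest reply is that nothing has been miscalculated. The stated power reproduces, and what is missing is an attrition assumption. That stands.

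Three further points also stand in part.

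- **Recruited or completed.** Table 1 places N=58 at the pre-test and post-test step, so one could read 58 as completers. Section III.C, however, calls it the number recruited, and no replacement rule would turn recruits into completers. The text at least needs to say which is meant.
- **Any dropout breaks the claim.** A reader might infer this from 58 being the minimum. It is true only for d = 0.375 and a two-sided test. Even then, the first lost pair costs about 0.7 percentage points (0.802 to 0.795), which has little practical weight. At 0.40, or one-sided, there is room for loss.
- **Aim 4 will have 70% power.** A reader might infer this from the retention figure. The documents do not support it. That figure is a lower bound from previous studies, stated under Aims 1 & 2, and is not a forecast for Aim 4. Aim 4 has a single follow-up at two weeks, reminders, and gift cards tied to the pre-test and post-test surveys (Section IV), so retention may well be better.

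It is also fair to say that Aim 4 is a one-group formative evaluation used to revise materials, and that no stopping decision depends on the test. This limits the consequence. It does not supply the missing allowance.

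**Conclusion.** The point holds as an unsupported margin, not as an arithmetic error. For a 1.5-point gain with SD 4.0 and a two-sided 0.05 test, the figure above 80% requires every one of the 58 recruits to complete both tests. Losses of 5% to 20% would bring power to between 78% and 70%, a shortfall of about 2 to 10 percentage points from the 80.2% available with no loss. If 0.40 is the intended effect size, the claim survives about 10% loss but not 20%.

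The conclusion rests on two-sided testing, on 58 being the number recruited, and on assumed loss rates. It concerns the knowledge score only. Severity is minor to moderate: the design is not invalidated, but the stated power should match the number of pairs likely to be analysed.

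**What to change.** In Section VI (Aims 3 & 4), state that 58 is the number recruited and that the test is two-sided (if so), and replace the single power figure with a range. For example:

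*With 58 survivors recruited, a two-sided 0.05 paired t-test and an SD of the difference of 4.0, power for a 1.5-point gain is 80% with 58 complete pairs, 78% with 55 (5% loss), 76% with 52 (10% loss) and 70% with 46 (20% loss, the edge of the retention seen in earlier studies). The gain detectable with 80% power runs from 1.50 to about 1.69 points. These retention rates are assumptions.*

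The same edit should say whether 1.5 points or an effect size of 0.40 is the target, and the N=58 label in Table 1 should be aligned with it.

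The cost is a few lines of text and a somewhat less favourable stated power; no extra participants are needed. Guaranteeing 58 complete pairs is a different and dearer choice: 58 / 0.90 gives 65 recruits at 10% loss, and 58 / 0.80 gives 73 at 20%.
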